## 12.2 Presentation of Plasma Concentrations and PK metrics

### Individual plasma concentration results:

A raw data listing will be provided displaying the concentration as reported, the result used in summary tables and mean time-concentration curves, and the change from pre-dose result. Results will be displayed using 3 significant digits.

### Summary statistics of plasma concentration table:

Summary statistics of the plasma concentration by treatment group and time point will be presented. In addition, the change from pre-dose will be summarized. Results will be displayed using 3 significant digits.

### PK metrics:

Summary statistics of PK metrics will be presented by treatment group. Results will be displayed using 3 significant digits.

Figures:

1. Mean concentrations versus nominal time by treatment group using the original (untransformed) scale of concentrations. The curves of each treatment group will be put into 1 graph, having an overlay plot in the end with 2 curves for each treatment group. (Samples from patients receiving placebo will not be analyzed by the laboratories that will be analyzing for dasiglucagon and GlucaGen®.)
2. Mean concentrations versus nominal time by treatment group using the log scale of concentrations. The curves of each treatment group will be put into 1 graph, having an overlay plot in the end with 2 curves for each treatment group. (Samples from patients receiving placebo will not be analyzed by the laboratories that will be analyzing for dasiglucagon and GlucaGen®.)
3. Individual dasiglucagon and glucagon concentrations versus nominal time curves using the original concentration scale overlaying all patients per treatment group will be prepared.

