Dasiglucagon (ZP4207) is a stable peptide analog of human glucagon, available in a ready-to-use liquid formulation and is in development for the treatment of severe hypoglycemia in insulin dependent patients with diabetes mellitus. Dasiglucagon is a specific and full glucagon receptor agonist designed to mimic the effects of glucagon, having a fast absorption and elimination (minutes). It is a peptide of 29 amino acids, with 7 amino acid substitutions compared to native glucagon. The main purpose of the substitutions is to increase the physical and chemical stability of the glucagon analog compared to marketed glucagon products such as Lilly's Glucagon or GlucaGen®. Dasiglucagon exhibits improved physical and chemical stability and is available in an aqueous solution at neutral pH.²

Five clinical trials have been completed with dasiglucagon: A first human dose trial (ZP4207-14013), a multiple-dose dose-escalation trial (ZP4207-15007) to evaluate the safety, tolerability, pharmacokinetics (PK) and pharmacodynamics (PD) of dasiglucagon, a phase 2 crossover trial to assess the PK and PD of a single dose of an optimized formulation of dasiglucagon administered subcutaneously (SC) in patients with T1DM (ZP4207-15126), and a feasibility trial testing the bionic pancreas with dasiglucagon was completed (ZP4207-16051).² Finally, a crossover trial (ZP4207-16098) assessing PK and PD responses after micro-doses of dasiglucagon administered SC to patients with type 1 diabetes mellitus under euglycemic and hypoglycemic conditions, compared to marketed glucagon, was completed.

Pharmacokinetics and pharmacodynamics of dasiglucagon

The results of the phase 1 and 2 clinical trials confirm dose-proportionality for dasiglucagon PK, which is characterized by a fast absorption with a peak plasma concentration obtained after 35 minutes. Thereafter, the plasma concentration rapidly declines with an average half-life of 28 minutes. The median time to the maximum plasma concentration (C_{max}) was later for dasiglucagon than for GlucaGen® (35 versus 20 minutes). For C_{max} , the results indicated that 0.3 mg dasiglucagon was comparable to 0.5 mg GlucaGen® (90% confidence interval: 0.8167; 1.0068) and 0.6 mg dasiglucagon was comparable to 1.0 mg GlucaGen® (90% confidence interval: 0.8850; 1.1991).² At these dose levels, the total exposures (AUC_{0-inf}) were higher for dasiglucagon compared to GlucaGen®.

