7.2 Discussion of trial design and choice of control groups

The trial will be randomized and double-blind to increase trial validity and to reduce bias during evaluation of assessments with the treatments. Since the 3 trial products are not identical in appearance, (dasiglucagon and placebo are liquid formulations and GlucaGen® is available as a powder for reconstitution), unblinded trial personnel, who will not be involved in other trial procedures and assessments, will do the handling, preparation and administration of trial product. Blinded trial personnel will do all trial assessments performed at the trial center.

Children with T1DM will be randomized 2:1:1 in order to evaluate the efficacy and safety of dasiglucagon compared to placebo and GlucaGen® and PK/PD parameters. The randomized, double-blind, parallel arm design with administration of a single dose of randomized trial product (dasiglucagon, placebo or GlucaGen®) will allow a relative comparison between the 3 treatment arms.

Dasiglucagon will be administered at fixed doses independent of body weight because this is the intended therapeutic dosing regimen in the emergency treatment of hypoglycemia. The selected dose of 1 mg GlucaGen® is the recommended dose for treatment of severe hypoglycemia (in accordance with the label, children below 25 kg body weight will be administered 0.5 mg GlucaGen®). Based on pre-clinical and clinical studies in adult patients, it has been demonstrated that 0.6 mg of dasiglucagon results in an initial PD response (i.e. acute glucose mobilization) comparable to 1 mg GlucaGen® (see also [Section 5.1](#)).

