7.3.1 Inclusion criteria

To be included in the trial, patients have to fulfill all of the following criteria:

1. Following receipt of verbal and written information about the trial, patient, parent(s) or guardian(s) of the patient must provide signed informed consent before any trial-related activity is carried out*
2. Female or male patients with T1DM for at least 1 year, diagnostic criteria as defined by the American Diabetes Association, and receiving daily insulin and in good and stable medical condition
3. At least 6.0 years of age (inclusive) and less than 18.0 years
Germany only: A “staggered approach” will be applied, whereby a positive safety assessment needs to be available for at least 10 patients who have completed the dosing visit in the overall trial before younger patients (6 to 11 years of age) may be enrolled.
4. Body weight ≥ 20 kg
5. Female patients must meet one of the following criteria:
 - a. Participant is of childbearing potential and agrees to use one of the accepted contraceptive regimens throughout the entire duration of the trial from screening until last follow-up visit. An acceptable method of contraception includes at least one of the following:
 - i. Abstinence from heterosexual intercourse
 - ii. Systemic contraceptives (birth control pills, injectable/implant/ insertable hormonal birth control products, transdermal patch); if the participant is using

- systemic contraceptives, she must use an additional form of acceptable contraception (iii or iv, below)
- iii. Intrauterine device (with and without hormones)
 - iv. Condom with spermicide
- or
- b. Participant is of non-childbearing potential due to pre-puberty status or a medical condition confirmed by the investigator
6. Male patients must meet the following criteria: If sexually active, uses condom and partner practices contraception during the trial from screening and until last follow-up visit
7. Willingness to adhere to the protocol requirements
- * Informed consent signatures must be obtained according to local regulations.

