### 3.2 Secondary Objective

- To confirm that a single dose of dasiglucagon [0.6 mg] is comparable to a single dose of GlucaGen® [1 mg/mL] in treating hypoglycemia in children with T1DM (in accordance with the label, children below 25 kg body weight will be administered 0.5 mg GlucaGen®)
- To assess safety profile of dasiglucagon in children with T1DM
- To assess pharmacokinetic (PK) profile of dasiglucagon in children with T1DM

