## 7. NOTATION OF TREATMENT GROUPS AND VISITS

### Notation of treatment groups

The following notation of **treatment groups** will be used throughout the report:

Full notation (as used in the study protocol)	Notation as used throughout all tables, listings, and figures
Dasiglucagon, liquid formulation, 1 mg/mL, 0.6 mL 1 mg lyophilized powder for reconstitution (GlucaGen®, Novo Nordisk)	dasiglucagon GlucaGen
Placebo treatment: Placebo, liquid formulation, 0.6 mL	Placebo

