#### 14.1.3 Trial medication administration

All details with regard to the trial medication administration will be listed.

A summary table will be prepared showing the number (percentage) of patients where the trial medication was administered.

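### GlucaGen PK summaries may pool 0.5 mg and 1 mg children in one column, and the PK table's Total column averages two different drugs

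*SAP*

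**What the plan says.** SAP 3.2 sets the comparator's dose by weight: "in accordance with the label, children below 25 kg body weight will be administered 0.5 mg GlucaGen". Protocol 7.4.9 repeats the rule, with 1 mg for all others. Protocol 7.3.1 admits children with "Body weight ≥ 20 kg", so the lower dose applies from 20 kg to just under 25 kg. For the test product, Protocol 7.2 says "Dasiglucagon will be administered at fixed doses independent of body weight because this is the intended therapeutic dosing regimen"; that dose is 0.6 mg.

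The PK reporting is organised by arm. SAP 12.2 says "Summary statistics of PK metrics will be presented by treatment group", and treats the concentration summaries and mean curves in the same way. The shell for Table 14.4.1.2 has three columns: dasiglucagon, GlucaGen and Total. The last follows the general rule in SAP 6 that summary tables carry a total column.

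The parameter list in SAP 12 has no dose-normalised Cmax or AUC. CL/f and Vz/f are formed from Dose and AUC0-inf, but Dose is not defined as the amount received. SAP 10.6 plans no subgroup analysis. For dosing, SAP 14.1.3 says "A summary table will be prepared showing the number (percentage) of patients where the trial medication was administered", alongside a per-patient listing of all administration details. SAP 7 gives the comparator's full notation as "1 mg lyophilized powder for reconstitution (GlucaGen®, Novo Nordisk" and does not mention 0.5 mg; the name it sets for outputs is simply GlucaGen.

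**The concern.** Cmax and AUC depend on dose. If some GlucaGen children receive half the dose of the others, a single mean or geometric mean for the arm mixes two dose levels, and no table shows how many children had which. The PK table is where the two products' exposures in children stand side by side. A reader will naturally compare the columns, because Protocol 5.1 discusses adult Cmax in dose pairs: "0.3 mg dasiglucagon was comparable to 0.5 mg GlucaGen", and likewise 0.6 mg with 1.0 mg. Below 25 kg the trial sets 0.6 mg against 0.5 mg, which is neither pair.

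Two smaller gaps go with this. Averaging dasiglucagon and glucagon, two analytes each matched to its own assay (Protocol 7.4.10), gives a Total that describes nothing. And if a programmer took 1 mg from the SAP 7 notation as Dose for every GlucaGen child, CL/f and Vz/f would be wrong for the lighter ones.

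What is at stake is how the descriptive PK tables can be read, not any test.

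**Working it through.** The plan states no figure for PK precision or for a PK comparison, so there is nothing to reproduce. Its one sizing figure, 90% power, concerns dasiglucagon against placebo and does not enter here.

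**Inputs.** The GlucaGen arm has 10 children (SAP 5). SAP 6 plans geometric means for all PK parameters except Tmax. Let k be the number on 0.5 mg. The documents do not give it. Protocol 7.4.9 requires at least 16 of 40 in each age group, so 16 to 24 are in the younger group; a quarter of these, 4 to 6, would fall in the GlucaGen arm if 2:1:1 holds within age. How many of them weigh under 25 kg is unknown, so k = 0 to 6 is an assumed range.

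**Dose effect alone.** Let r be exposure at 0.5 mg relative to 1 mg in the same child. The pooled geometric mean is r^(k/10) times that of an all-1 mg arm, so the dasiglucagon/GlucaGen ratio is multiplied by r^(-k/10). With dose-proportional GlucaGen, r = 0.5 and the multiplier is 2^(k/10). The documents state dose-proportionality only for dasiglucagon.

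A second value of r for Cmax comes from the adult intervals in Protocol 5.1, taking geometric midpoints:
- 0.3 mg v 0.5 mg: √(0.8167 × 1.0068) = 0.907
- 0.6 mg v 1.0 mg: √(0.8850 × 1.1991) = 1.030
- with dasiglucagon dose-proportional, r = 0.5 × 1.030 / 0.907 = 0.568

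| k of 10 | Pooled GlucaGen mean v all-1 mg, r = 0.5 | Ratio multiplier, r = 0.5 | Ratio multiplier for Cmax, r = 0.568 |
|---|---|---|---|
| 0 | 1.00 | 1.00 | 1.00 |
| 1 | 0.93 | 1.07 | 1.06 |
| 2 | 0.87 | 1.15 | 1.12 |
| 3 | 0.81 | 1.23 | 1.18 |
| 6 | 0.66 | 1.52 | 1.40 |

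Reading the multiplier as the whole shift in the ratio also requires weight to be balanced between arms. Protocol 7.4.9 stratifies by age group and injection site, not by weight.

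**Pooled mean against the 1 mg children actually in the arm.** This is a different question, because the 0.5 mg children are lighter and the plan's own model scales clearance by weight. Take a 22.5 kg child on 0.5 mg, a 1 mg child of weight W, and clearance proportional to weight to the power 0.75 or 1 (my assumptions). Then r = 0.5 × (W/22.5)^b:
- W = 25 kg: r = 0.54 to 0.56; pooled factor at k = 3 is 0.83 to 0.84
- W = 43.2 kg: r = 0.82 to 0.96; pooled factor 0.94 to 0.99
- W = 61.2 kg: r = 1.06 to 1.36; pooled factor 1.02 to 1.10

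The last two weights are means of the modelling groups in Protocol 5.2. At k = 3 the shift runs from about −17% to +10%, so its sign is not fixed.

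**CL/f and Vz/f.** If 1 mg were entered as Dose for a child given 0.5 mg, that child's two values would double, and the arm's geometric mean would rise by 2^(k/10): 7%, 15% and 23% for k = 1, 2 and 3.

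**The case against.** The strongest reply is that the comparator is the weight-based label regimen by design. The secondary objective itself contains the 0.5 mg rule, so a pooled column describes the regimen as given, and an all-1 mg arm is a reference the trial never intended. The lower dose also goes only to the lightest children: 0.5 mg at 20 to 25 kg is 0.025 to 0.020 mg/kg, the same as 1 mg at 40 to 50 kg. CL/f is already the reciprocal of dose-normalised AUC0-inf. Administration details, body measurements, concentrations and PK metrics are all listed per patient, so dose can be traced.

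Most of this stands, and it limits the point to presentation. It does not help someone reading the summary tables: Cmax, AUC0-30min and AUC0-300min have no dose-adjusted counterpart, and the number on each dose is not tabulated.

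A reader might infer three stronger things that the documents do not support:
- That the outputs present these data as 1 mg data. They do not; the 1 mg wording is in the full-notation column of SAP 7, and tables use GlucaGen.
- That a planned exposure contrast is biased. SAP 12 plans descriptive statistics only, with no ratio, interval or test between products, and the PK objective is the dasiglucagon profile. The adult pairings concern Cmax; Protocol 5.1 says AUC0-inf at those doses was higher for dasiglucagon.
- That the recovery comparison with GlucaGen needs restricting to 25 kg and above. The comparability objective includes the 0.5 mg rule, and such a subset would add a subgroup to a plan that has none and shrink an arm of 10.

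**Conclusion.** The point holds as a minor reporting gap. The GlucaGen PK summaries can blend two doses without showing it, and the Total column in Table 14.4.1.2 is meaningless as specified.

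The +7% to +23% for k = 1 to 3 describes a ratio that a reader may form from adjacent columns, relative to an all-1 mg arm. It rests on dose-proportional GlucaGen, balanced weight and an assumed k; if no child under 25 kg is randomised to GlucaGen, the blending does not arise. It should not be read as a demonstrated distortion, since the pooled mean could lie on either side of the mean of the 1 mg children. The primary analysis, the testing hierarchy and the sample size are unaffected. Nothing here bears on which doses should be given.

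**What to change.** In SAP 12 and Tables 14.4.1.1 to 14.4.1.4:
- present GlucaGen concentrations and PK metrics by dose received, showing individual values where few children had 0.5 mg, or add dose-normalised Cmax and AUCs;
- state that Dose in CL/f and Vz/f is the dose actually received;
- delete the Total column from Table 14.4.1.2, as an exception to the general rule in SAP 6.

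Elsewhere, show the number of children on each GlucaGen dose in Table 14.3.4.3, and add the 0.5 mg dose to the full notation in SAP 7 so that it agrees with SAP 3.2.

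The cost is a few sentences and some table-shell edits, using data already collected. The drawback is that the 0.5 mg group may be too small to summarise; dose-normalised values or a short listing would then have to serve.

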### 13. PHARMACODYNAMIC ENDPOINTS

Plasma glucose is determined at pre-dose and at 4, 6, 8, 10, 12, 15, 17, 20, 30, and 45 minutes (and as well at 60 minutes if the patient's body weight is  $\geq 21$  kg) after dosing. The actual time of blood sampling should not deviate from the nominal time by more than  $\pm 30$  seconds until the 20-minute collection time point, and by more than  $\pm 1$  minute for the subsequent collection time points. Pre-dose is defined as within 2 minutes prior to dosing

The pharmacodynamic endpoint is the plasma glucose response as area under the effect curve above baseline from time 0 to 30 minutes ( $AUE_{0-30min}$ ).  $AUE_{0-30min}$  will be calculated using SAS software.

Individual plasma glucose concentration results:

A raw data listing will be provided displaying the concentration as reported, the result used in summary tables and mean time-concentration curves and the change from pre-dose result.

Summary statistics of plasma glucose concentration table:

Summary statistics of the plasma glucose concentration by treatment group and time point will be presented. In addition, the change from pre-dose will be summarized.

Pharmacodynamic metrics:

Summary statistics of pharmacodynamic metrics will be presented by treatment group.

Figures:

1. Mean glucose concentrations versus nominal time by treatment group using the original (untransformed) scale of concentrations. The curves of each treatment group will be put into 1 graph, having an overlay plot in the end with 2 curves for each treatment group.
2. Individual glucose concentrations versus nominal time curves using the original concentration scale overlaying all patients per treatment group will be prepared.

## 14. SAFETY ANALYSES

All safety analyses will be based on the safety set.

### 14.1 Extent of Exposure

#### 14.1.1 Insulin administration prior to the hypoglycemia induction procedure

All details with regard to insulin administration prior to the hypoglycemia induction procedure will be listed. This includes whether the patient used multiple daily injections, long-acting insulin, short-acting insulin (except insulin glulisine [Apidra®]), insulin NPH, or insulin glulisine (Apidra®) or an insulin pump.

A summary table will be prepared showing the number (percentage) of patients who used any of the following:

- Multiple daily injections
- Insulin NPH
- Insulin pump
- Insulin glulisine (Apidra®)

#### 14.1.2 Hypoglycemia induction procedure

All details with regard to the hypoglycemia induction procedure will be listed.

A summary table will be prepared showing the number (percentage) of patients where the hypoglycemia induction procedure was performed, the total amount of insulin administered to induce hypoglycemia and the total amount of glucose administered during the induction procedure.

#### 14.1.3 Trial medication administration

All details with regard to the trial medication administration will be listed.

A summary table will be prepared showing the number (percentage) of patients where the trial medication was administered.

#### 14.1.4 Post-treatment rescue glucose infusion

All details with regard to the post-treatment rescue glucose infusion will be listed. A summary table will be prepared showing the number (percentage) of patients where glucose was given as rescue medication.

The time to first IV glucose infusion, after IMP administration (IV glucose infusion prior to IMP administration should not be included, as it is part of hypoglycemic clamp procedure) will be described with descriptive statistics. No statistical tests will be performed.

Time to first IV glucose infusion [minutes] is calculated as:

Time of start of first glucose administration – Time of administration of study medication.  
No censoring is done in case no IV glucose infusion is given, ie, the descriptive statistics only show data when an infusion was given.

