- Plasma glucose changes from baseline within 30 minutes, within 20 minutes, within 15 minutes, and within 10 minutes after study drug injection or at the time of rescue IV glucose.

Safety endpoints

- AEs
- Clinical laboratory assessments (biochemistry, hematology, coagulation, urinalysis)
- Vital signs
- Physical examination
- Clinically significant changes in the electrocardiogram
- Local tolerability
- Administration of rescue IV glucose infusion after trial product injection
- Time to first IV glucose infusion, after trial product administration (N.B. IV glucose infusion prior to trial product administration should not be included, as it is part of hypoglycemic clamp procedure)
- Immunogenicity endpoint: occurrence of ADAs

Pharmacokinetic endpoints

PK endpoints will be derived from plasma dasiglucagon and GlucaGen® profiles from 0 to 300 minutes:

- Area under the plasma dasiglucagon or GlucaGen® concentration versus time curve from 0 to 30 minutes post-dose ($AUC_{0-30min}$)

- Area under the plasma dasiglucagon or GlucaGen® concentration versus time curve from 0 to 300 minutes post-dose ($AUC_{0-300min}$)
- Area under the plasma dasiglucagon or GlucaGen® concentration versus time curve from 0 to infinitely post-dose (AUC_{0-inf})
- Maximum of all valid plasma dasiglucagon or GlucaGen® concentration measurements from 0 to 300 minutes post-dose (C_{max})
- Time to maximum of plasma dasiglucagon or GlucaGen® concentration measurements (t_{max})
- Terminal elimination rate constant of plasma dasiglucagon or GlucaGen® (λ_z)
- Terminal plasma elimination half-life of dasiglucagon or GlucaGen® ($t_{1/2}$)
- Total body clearance of plasma dasiglucagon or GlucaGen® (CL/f)
- Volume of distribution of plasma dasiglucagon or GlucaGen® (V_z/f)
- Mean residence time of plasma dasiglucagon or GlucaGen® (MRT)

Pharmacodynamics endpoint

- Plasma glucose response as area under the effect curve above baseline from time zero to 30 minutes, $AUE_{0-30min}$

7. Investigational plan

[figure not shown]

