7.4.5.2.3 Rescue provisions for hypoglycemia

During insulin-induced hypoglycemia, plasma glucose levels as well as the patient status will be monitored closely throughout the procedure. After administration of trial product, if their glucose

levels become too low, patients may receive post-treatment IV glucose infusion to ameliorate hypoglycemia, as follows:

1. The IV glucose infusion should be initiated if a patient experiences escalating symptoms of hypoglycemia (e.g. start of moderate symptoms of hypoglycemia) at any time during the test procedure. Glucose infusion should then be initiated targeting a plasma glucose level >70 mg/dL
2. If plasma glucose is <54 mg/dL between t=8 and t=44 minutes, glucose infusion (e.g. 1-2 mg/kg administered over 5-10 seconds) should be initiated to maintain plasma glucose between 55 mg/dL and 70 mg/dL. Pause glucose infusion if plasma glucose is >70 mg/dL
3. If plasma glucose is <70 mg/dL at t \geq 45 minutes, glucose infusion (e.g. 2-3 mg/kg administered over 5-10 seconds) should be initiated to maintain plasma glucose between 70 mg/dL and 90 mg/dL. Pause glucose infusion if plasma glucose is >80 mg/dL

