Clinical Study Report Section 14  
Page 1 of 1

14.3.4.3: Trial medication, Safety analysis set

	dasiglucagon (N=xxx)	Placebo (N=xxx)	GlucaGen (N=xxx)	Total (N=xxx)
Was the trial medication administered?				
No	n ( xx.x%)	n ( xx.x%)	n ( xx.x%)	n ( xx.x%)
Yes	n ( xx.x%)	n ( xx.x%)	n ( xx.x%)	n ( xx.x%)
Missing	n	n	n	n

PROGRAM SOURCE:###, DATA CUT OFF DATE: ddmmyyyy

RUN DATE: ddmmyyy hh:mm CET

14.3.4.4: Post-treatment rescue glucose infusion, Safety analysis set

	dasiglucagon (N=xxx)	Placebo (N=xxx)	GlucaGen (N=xxx)	Total (N=xxx)
Was glucose given for rescue?				
No	n ( xx.x%)	n ( xx.x%)	n ( xx.x%)	n ( xx.x%)
Yes	n ( xx.x%)	n ( xx.x%)	n ( xx.x%)	n ( xx.x%)
Missing	n	n	n	n
Time to first IV glucose infusion [min]				
Mean (SD)	n	xx	xx	xx
Median	Mean (SD)	xx.x (xx.xx)	xx.x (xx.xx)	xx.x (xx.xx)
Min, Max	Median	xx.x	xx.x	xx.x
	Min, Max	xx, xx	xx, xx	xx, xx

PROGRAM SOURCE:###, DATA CUT OFF DATE: ddmmmyyyy

RUN DATE: ddmyyy hh:mm CET

14.3.5.1.1: ECG, overall interpretation, Safety analysis set

Visit	Time Point	Result	dasiglucagon (N=xxx)	Placebo (N=xxx)	GlucaGen (N=xxx)	Total (N=xxx)
Screening		NORMAL	n ( xx.x%)	n ( xx.x%)	n ( xx.x%)	n ( xx.x%)
		ABNORMAL / NOT CLIN. SIG.	n ( xx.x%)	n ( xx.x%)	n ( xx.x%)	n ( xx.x%)
		ABNORMAL / CLIN. SIG.	n ( xx.x%)	n ( xx.x%)	n ( xx.x%)	n ( xx.x%)
Dosing	Pre-dose	NORMAL	n ( xx.x%)	n ( xx.x%)	n ( xx.x%)	n ( xx.x%)
		ABNORMAL / NOT CLIN. SIG.	n ( xx.x%)	n ( xx.x%)	n ( xx.x%)	n ( xx.x%)
		ABNORMAL / CLIN. SIG.	n ( xx.x%)	n ( xx.x%)	n ( xx.x%)	n ( xx.x%)
Dosing	20min post dose	NORMAL	n ( xx.x%)	n ( xx.x%)	n ( xx.x%)	n ( xx.x%)
		ABNORMAL / NOT CLIN. SIG.	n ( xx.x%)	n ( xx.x%)	n ( xx.x%)	n ( xx.x%)
		ABNORMAL / CLIN. SIG.	n ( xx.x%)	n ( xx.x%)	n ( xx.x%)	n ( xx.x%)
Dosing	35min post dose	NORMAL	n ( xx.x%)	n ( xx.x%)	n ( xx.x%)	n ( xx.x%)
		ABNORMAL / NOT CLIN. SIG.	n ( xx.x%)	n ( xx.x%)	n ( xx.x%)	n ( xx.x%)
		ABNORMAL / CLIN. SIG.	n ( xx.x%)	n ( xx.x%)	n ( xx.x%)	n ( xx.x%)
Dosing	45min post dose	NORMAL	n ( xx.x%)	n ( xx.x%)	n ( xx.x%)	n ( xx.x%)
		ABNORMAL / NOT CLIN. SIG.	n ( xx.x%)	n ( xx.x%)	n ( xx.x%)	n ( xx.x%)
		ABNORMAL / CLIN. SIG.	n ( xx.x%)	n ( xx.x%)	n ( xx.x%)	n ( xx.x%)
Dosing	60min post dose	NORMAL	n ( xx.x%)	n ( xx.x%)	n ( xx.x%)	n ( xx.x%)
		ABNORMAL / NOT CLIN. SIG.	n ( xx.x%)	n ( xx.x%)	n ( xx.x%)	n ( xx.x%)
		ABNORMAL / CLIN. SIG.	n ( xx.x%)	n ( xx.x%)	n ( xx.x%)	n ( xx.x%)
Dosing	300min post dose	NORMAL	n ( xx.x%)	n ( xx.x%)	n ( xx.x%)	n ( xx.x%)

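### Time to first post-dose IV glucose is summarised only in children who received it, so the by-arm mean and median describe groups selected by outcome and can point opposite to the rescue risk

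*SAP*

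**What the plan says.** Protocol Section 6 lists, among the safety endpoints, "Time to first IV glucose infusion, after trial product administration". The endpoint just before it in that list is whether rescue IV glucose was given at all. Protocol 10.1.4 says only that the time will be described, without tests.

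The restriction to rescued children comes from SAP 14.1.4. That section defines the time as start of first glucose minus time of dosing, and then states: "No censoring is done in case no IV glucose infusion is given, ie, the descriptive statistics only show data when an infusion was given". It also says "No statistical tests will be performed", and it provides for the incidence: "A summary table will be prepared showing the number (percentage) of patients where glucose was given as rescue medication".

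The layout of Table 14.3.4.4 has one column per arm. Its first block is "Was glucose given for rescue", with n (%). Below it come n, mean (SD), median, minimum and maximum of the time in minutes.

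Protocol 7.4.5.2.3 sets the triggers. One applies at any time: "The IV glucose infusion should be initiated if a patient experiences escalating symptoms of hypoglycemia". The others depend on plasma glucose: below 54 mg/dL "between t=8 and t=44 minutes", and below 70 mg/dL from 45 minutes on.

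**The concern.** This is a time-to-event variable, and the children with the best outcome, those who never need rescue, are left out of its summary. Whether a child is rescued depends on the glucose and symptoms that follow the injection, so the subset summarised in each arm is chosen by a consequence of treatment. Randomisation no longer makes those subsets comparable.

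The layout sets the arm means and medians next to each other, which invites the reading that a longer time is better. An arm in which one child is rescued early can look worse than an arm in which most children are rescued later.

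The SAP does not treat its primary endpoint this way. Under SAP 11.1, children who do not recover stay in the analysis and are censored at 45 minutes.

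**Working it through.** **The plan's own figure.** None is stated for this endpoint. The only design figure is 90% power for the primary log-rank test (SAP 5): 20 v 10 children, exponential medians of 10 and 50 minutes, 45 minutes of follow-up, two-sided 5%. The Lakatos method gives Z = 3.244, and Φ(3.244 − 1.960) = 90.0%. The figure reproduces, and nothing below touches it.

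**Inputs.** The arm sizes of 20 and 10 come from SAP 5. Rescue rates and times are assumptions, because the documents give none.

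**Illustration.** Dasiglucagon: 1 of 20 rescued, at 10 minutes. Placebo: 6 of 10 rescued, at a mean of 35 minutes, all before 45 minutes.

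- Rescued-only mean (SAP rule): 10 v 35 minutes. Placebo looks better.
- Percentage rescued: 1/20 = 5% v 6/10 = 60%. Dasiglucagon is better.
- Mean rescue-free time to 45 minutes, all children kept: (10 + 19 × 45)/20 = 43.25 v (6 × 35 + 4 × 45)/10 = 39.0 minutes. Dasiglucagon is better.

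A second assumed data set, with placebo rescues at 12, 20, 30, 40 and 44 minutes and the dasiglucagon arm as before, behaves the same way. The rescued-only means are 10 v 146/5 = 29.2 minutes. With all children kept they are 43.25 v (146 + 5 × 45)/10 = 37.1 minutes.

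**How often the direction is wrong.** Trials of 20 v 10 children over 45 minutes were simulated, 10,000 per setting, with the true rescue risk always lower on dasiglucagon. Rescue times followed either a constant hazard or a uniform distribution over 8 to 45 minutes. Entries are the percentage of trials in which the summary favours placebo, among trials with at least one rescue in each arm.

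| Risk, dasiglucagon v placebo | Rescued-only mean, constant hazard | Rescued-only mean, uniform | All children kept, constant hazard | All children kept, uniform |
|---|---|---|---|---|
| 5% v 30% | 46.7 | 49.8 | 7.7 | 8.1 |
| 5% v 50% | 44.2 | 50.2 | 1.0 | 1.4 |
| 5% v 80% | 33.8 | 49.7 | 0.0 | 0.0 |
| 10% v 30% | 47.2 | 49.6 | 12.9 | 13.9 |
| 10% v 50% | 43.6 | 49.7 | 2.0 | 2.7 |
| 10% v 80% | 30.8 | 49.1 | 0.0 | 0.1 |
| 20% v 30% | 48.2 | 50.4 | 29.8 | 30.8 |
| 20% v 50% | 42.5 | 49.6 | 7.4 | 9.0 |
| 20% v 80% | 28.0 | 50.5 | 0.1 | 0.6 |

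With uniform times, the distribution among rescued children is the same in both arms whatever the risks, so the rescued-only mean is a coin toss. With all children kept, errors remain mainly where the risks are close and the arms are small.

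**Empty row.** The chance of no dasiglucagon rescue is (1 − p)^20: 36%, 12% and 1% at p = 5%, 10% and 20%. That arm's time row would then be blank.

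**The case against.** The strongest reply is that the table already gives the missing context. The n (%) rescued stands directly above the time rows, and those rows carry their own n. In the illustration a reader would see 1 (5.0%) v 6 (60.0%) first, then times with n = 1 and n = 6. Incidence is also a separate named endpoint, and every infusion is listed. The conditional basis is stated openly, no test is planned, and rescue is handled explicitly in the primary and responder analyses. All of this stands and limits the weight of the point. It does not make a rescued-only mean or median a valid description of time to rescue by arm.

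The illustration is also a chosen case. In phase 2, all adults at all doses reached at least 70 mg/dL and rose by at least 20 mg/dL within 30 minutes (Protocol 5.1). An empty dasiglucagon row is therefore plausible, and then nothing reverses.

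Three stronger readings are tempting and are not supported:

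- A reader might infer that the planned table hides the difference in rescue. It does not, because the n (%) row shows it.
- A reader might infer that many infusions will come at or after 45 minutes, mainly on placebo, since the glucose threshold rises there. The documents give no rescue rates by arm or time. Failure to rise by 20 mg/dL is also not the same as being below 70 mg/dL, because children are dosed at 54 to below 80 mg/dL.
- A reader might call the subsets self-selected. They are selected by protocol triggers acting on post-dose glucose and symptoms.

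**Conclusion.** The point holds for the time rows of Table 14.3.4.4 and no further. SAP 14.1.4 conditions a named safety endpoint on a post-dose outcome, and the resulting by-arm mean and median can run opposite to the rescue risk. Under the assumed risks (dasiglucagon 5 to 20%, placebo 30 to 80%), they did so in 28 to 48% of simulated trials with a constant hazard and in about half with uniform times. The corresponding range with all children kept was 0 to 31%, and 9% or less when the placebo risk was at least 50%. These percentages rest on assumed rates and times and count only trials with a rescue in both arms. They show what the summary can do; they do not predict this trial.

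Type I error, power and the primary conclusion are unaffected. The change is worth making because the endpoint is named and will be reported by arm. The efficacy claim does not depend on it.

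**What to change.** In SAP 14.1.4, replace the no-censoring rule with a Kaplan-Meier (cumulative incidence) summary of time to first post-dose IV glucose by arm, in the whole safety analysis set. Censor non-rescued children at a stated end of observation: 300 minutes, where the glucose monitoring in Protocol 7.4.5.2.2 ends, or earlier if the child's observation ends earlier.

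Report the percentage rescued before 45 minutes separately from the percentage rescued at or after 45 minutes. The protocol's glucose threshold changes there, so a single curve to 300 minutes spans two rescue rules. Where fewer than half of an arm are rescued, show the median as not reached and let the percentages carry the result.

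Keep the n (%) row. If the mean and median among rescued children are retained, label them in Table 14.3.4.4 as conditional on rescue and not a comparison of randomised groups.

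The cost is one extra descriptive output from infusion times already collected. No test, sample size or trial procedure changes.
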